## Protocol Synopsis

### *Brief Summary*

We will conduct a parallel-arm, double-blind individually randomized control trial (RCT) in 30 healthy older adults, where attentional control demands in working memory training will be systematically increased using engaging game-based simulations. There are three parallel arms. The first two arms use experimenter-designed simulation games, where participants will be trained on either predictable low attentional control (Arm 1: Low-C) or unpredictable high attentional control (Arm 2: High-C) working memory games. The third arm uses a commercially-available strategy video game requiring highest level of attentional control (Arm 3: High-C+), by adding multi-tasking to the unpredictable attentional shifts in working memory. In all three training arms, neural and cognitive changes in both near and far tasks will be examined immediately after the 8-week long intervention. Long-term cognitive changes will also be assessed at 6 months after completion of training. The far and near cognitive domains that will be examined in this RCT are episodic memory (the primary cognitive outcome, and a marker of early stages of AD) and executive control (the secondary cognitive outcome). We expect that the high attentional control training arms will greatly improve both primary and secondary cognitive outcomes in older adults not only immediately after the training, but also at the +6-month period. We also expect cognitive frailty to interact with the extent to which attentional control is trained.

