Additionally, a single-session, baseline functional neuroimaging data-set will be collected in a control group of 18 younger adults. These younger adults will not undergo any training. High attentional control training arms (High-C and High-C+) are also expected to heighten compensatory brain activation in older adults after intervention, for both episodic memory (primary outcome) and executive control (secondary outcome) in-scanner tasks, paralleling the baseline activity of younger brains. These high attentional control training arms are also expected to positively impact brain structures that progressively decline with aging. The data from younger adults, our functional control group, will provide critical information about the brain regions activated in young, healthy brains during episodic memory (far transfer) and executive functions (near transfer). It will also help us determine whether older adults' brain activity following training resembles that of younger brains.

The primary objectives of this double-blind RCT are to evaluate the efficacy of high attentional control training on episodic memory (primary cognitive outcome) in an older adult population, by evaluating a) immediate training-related

changes in performance and neural activation during episodic memory tasks, and b) long-term changes at a +6-month retention period in performance during episodic memory tasks. The secondary objective of this RCT is to evaluate the efficacy of high attentional control training on executive functions (secondary cognitive outcome) in an older adult population by evaluating neuro-cognitive changes in executive functions immediately after the training, and cognitive gains at +6-month retention period.

In order to achieve these objectives, cognitive measures of both primary and secondary outcomes will be collected in healthy older adults at before training (baseline), immediately after 8 weeks of training (immediate post-training), and 6 months after training completion. MRI scanning, including fMRI tasks of episodic memory (primary outcome) and executive functions (secondary outcome), will be conducted at baseline and at immediate post-training for older adults, and only once in younger adults.

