### **Study Design**

**Overview.** This parallel arm, individually randomized control trial (RCT) will recruit 34 older adults from Dallas and neighboring counties. We aim to retain at least 30 participants on whom immediate post-training gains in both *near* and *far* abilities can be observed. This RCT shall be registered at [ClinicalTrials.gov](https://clinicaltrials.gov). There will be a Clinical Coordination Team (co-directed by [name] and the Project Manager) that will implement the intervention and check in with the participants on a weekly basis regarding their training progress. A blinded data collection team, directed by a post-doctoral fellow, will collect both behavioral and neuroimaging assessments before and after training. There will also be

a Data Coordination Team (co-directed by [name] and a post-doctoral fellow) that will be responsible for scoring and preprocessing the data. All data will be deposited in a HIPAA compliant server at the PI's laboratory. The team leaders will meet twice a month and each team will meet weekly to oversee any issues with subject recruitment, logistics and data collection. We will also recruit a total of 20 younger adults (YA, 18-30 years of age) for neuroimaging, who will be the functional controls for the older adults in the RCT.

This is a Phase 1 trial with multiple interventions in older adults, where the goal is to compare high attentional control trainings (High-C and High-C+) to low attentional control training (Low-C) and evaluate training-related changes in neurocognitive functions of both near (secondary outcome) and far transfer (primary outcome) tasks.

***Experimental Design.*** There are three intervention arms for older adults (OA) in this RCT trial, where attentional control demands in working memory training will be systematically increased using engaging game-based simulations.

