***Sample Size Justification for the older adults in the RCT.*** We estimated the power (using G\*power3.1) to detect the differences between the Training Arm (3) x Assessment (2) interaction on the primary cognitive outcome. *The current study is the first phase of a larger randomized controlled trial. We calculate our power for the full trial, but our requested sample size for this study is 51.* We will recruit 177 older adults with the aim to retain a total sample size of 144 older adults at immediate post-training with the expected attrition of 18%. We report two expected effect sizes of Cohen's *f* for our calculations. One,  $f=.35$ , the minimum effect size obtained across our 3 pilot studies. Another,  $f=.16$ , based on a meta-analysis on computer-based cognitive training in older adults. The proposed total sample size of 144 older adults will provide us with >93% power to detect the Training Arm (3: Low-C, High-C, High-C+) x Assessment

(A vs. B) interaction at  $f=.16$  and  $>98\%$  power to detect the interaction at  $f=.35$  on the primary cognitive outcome at  $p<.05$ . It will also provide  $>90\%$  power to detect a meaningful between-group difference ( $f=.35$ ) at immediate post-testing, after controlling for baseline cognition, at  $p<.05$ . At +6mo retention period (Assessment C), we expect to retain a total of 117 older adults, after the expected  $\sim 20\%$  attrition between Assessments B and C. This will provide us with  $>87\%$  power to detect the Training Arm (3: Low-C, High-C, High-C+) x Assessment (2: A vs. C) interaction at  $p<.05$  at  $f=.16$ . We will conduct 2 ANOVAs, one for primary and one for secondary. Our proposed sample size will provide us with sufficient power ( $>87\%$ ) to detect the Training Arm (3) x Assessment (2) interaction at a corrected  $p$  value of .025 ( $=.05/2$  for 2 cognitive outcomes of interest).

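### The sample size section puts this study at 51, against 34 recruited and 30 retained elsewhere, and no power is stated for the 30 to be analysed

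*Combined protocol and SAP*

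**What the plan says.** All places are in the combined protocol and SAP.

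- **Study Design, Sample Size Justification for the older adults in the RCT.** This study is described as the first phase of a larger randomised trial. The section then states: "We calculate our power for the full trial, but our requested sample size for this study is 51". The figures that follow belong to the full trial: "We will recruit 177 older adults with the aim to retain a total sample size of 144 older adults at immediate post-training". At six months, "we expect to retain a total of 117 older adults", after roughly 20% "attrition between Assessments B and C". The planning effects are f=.35 (the smallest across three pilot studies) and f=.16 (from a meta-analysis). For f=.16 at the .05 level, the stated power is above 93% with 144 and above 87% with 117.
- **Brief Summary.** The trial is an "individually randomized control trial (RCT) in 30 healthy older adults".
- **Study Design, Overview.** The trial "will recruit 34 older adults from Dallas and neighboring counties. We aim to retain at least 30 participants" with observable gains immediately after training.
- **Study timeline for Year 1.** Data collection on 25 younger adults and 26 older adults (10, 10 and 6 by arm) is to be completed in the first year.
- **Objective (Brief Summary).** "The primary objectives of this double-blind RCT are to evaluate the efficacy of high attentional control training on episodic memory".
- **Data Analysis Plan.** The interaction of Training Arm (3) with Assessment (2) is the effect of main interest. The two ANOVAs, one per cognitive outcome, are each tested at .025.

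**The concern.** There are two separate gaps.

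First, the size of this study is not consistent. The Brief Summary and the Overview agree on 30 older adults retained, from 34 recruited. The section that should justify that number gives 51 under a heading about older adults, without saying what 51 counts.

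Second, the plan sets an efficacy objective and a formal test at .025 for this phase, but every power figure rests on the full trial's size. A reader cannot tell from the plan what 30 participants in three arms can detect. The practical risk lies in interpretation: a non-significant interaction in this phase could be taken as evidence against the training when an effect as large as the plan's own meta-analytic value had little chance of being detected.

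**Working it through.** **1. What 51 could be.**
- Attrition does not link 51 to 30. That would be a loss of (51 − 30)/51 = 41%, against the 18% assumed for the full trial. The Overview's own figures imply (34 − 30)/34 = 11.8%.
- The year-1 counts do sum to it: 25 younger + 26 older = 51. The plan never makes this link. If it is meant, 51 includes untrained younger controls, and 26 older adults still differs from 34 and 30.

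**2. Inputs for power.** There are k=3 arms and m=2 assessments. The effects are f=.16 and f=.35 (Sample Size Justification), alpha is .025 (Data Analysis Plan), and N=30 is the number retained (Overview). The correlation ρ between assessments is not in the document and is an assumption.

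**3. Formula.** Repeated-measures ANOVA, within-between interaction, by the noncentral F distribution:
- λ = f² × N × m/(1 − ρ)
- df = (k − 1)(m − 1) = 2 and (N − k)(m − 1) = N − 3

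**4. Reproducing the plan's figures (alpha .05, ρ=.5).**
- N=144, f=.16: λ = .0256 × 144 × 2/.5 = 14.75, power 93.5% (stated above 93%).
- N=144, f=.35: power above 99.9% (stated above 98%).
- N=117, f=.16: λ = .0256 × 117 × 2/.5 = 11.98, power 87.4% (stated above 87%).

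Reading the two f=.16 statements as 93–94% and 87–88% implies ρ of .489–.510 and .495–.509. So ρ=.5 is a reasonable guess at what the sponsor used. I show .3 to .7 around it.

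**5. The same calculation for this phase (N=30, alpha .025, df 2 and 27).** At ρ=.5, λ = .0256 × 30 × 4 = 3.07 for f=.16, and .1225 × 30 × 4 = 14.70 for f=.35.

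| Quantity | ρ=.3 | ρ=.5 | ρ=.7 |
|---|---|---|---|
| Power, f=.16 | 14.3% | 20.2% | 34.9% |
| Power, f=.35 | 68.6% | 84.6% | 97.9% |
| Minimum detectable f, 80% power | .39 | .33 | .26 |

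At f=.35, power reaches 80% once ρ is about .44.

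**6. Six months (illustrative).** If the full trial's loss of about 20% between B and C also applied here, which is an assumption, 30 × .8 = 24 would remain. At alpha .025, power would be 15.4% (11.2 to 26.3%) at f=.16 and 72.3% (55.0 to 93.0%) at f=.35.

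**The case against.** The strongest reply is that nothing is hidden or miscalculated. The section says openly that power is for the full trial and that this study is its first phase. The Overview calls it Phase 1, and the timeline describes the year-1 data as pilot data to show that the trial can be conducted. A first phase need not be powered for the smaller planning effect. At the pilot effect, 30 participants give about 85% power at ρ=.5, even at .025. The 51 also has a plausible source in the year-1 counts.

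Most of this stands. A reader might infer that full-trial power is being passed off as this study's, or that the stated power is wrong. The document supports neither inference: the scope is disclosed and the figures reproduce. A reader might also infer that this phase is underpowered across the board. That does not follow either, because the shortfall at immediate post-training is clear at f=.16, whereas at f=.35 it arises only if ρ is below about .44. Nor can 51 be taken as a number of older adults retained, since the plan does not say so.

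The reply does not close the two gaps. The year-1 explanation of 51 is never stated and would add a third older-adult count. Disclosing that the power belongs elsewhere also leaves this phase's efficacy test with no statement of what it can detect.

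**Conclusion.** The point holds as an inconsistency and a reporting gap, and should be fixed. The 51 is not reconciled with the 30 in the Brief Summary, the 34 and 30 in the Overview, or the 26 older adults in the timeline. No power is given for the sample on which the interaction will be tested.

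At 30 analysed and alpha .025, power is about one in five at the meta-analytic effect and about 85% at the pilot effect, and the smallest detectable f (.33) lies just below the pilot value. These figures assume ρ=.5, which the document does not state but which reproduces its full-trial power, and they assume that the 30 retained are the number analysed. Over ρ from .3 to .7, power at f=.16 stays at or below 35%, so the conclusion for that effect does not depend on the choice. The conclusion for f=.35 does.

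**What to change.** 1. Correct 51, or say what it counts, and reconcile it with the Brief Summary, the year-1 timeline and the Overview.
2. Label 177, 144 and 117, and the power attached to them, as the full trial's, with this study as its first phase.
3. State power and minimum detectable f at N=30 for f=.16 and f=.35 at alpha .025, with the assumed ρ and a range. Optionally add the same at the number expected at Assessment C, with its attrition assumption.
4. Say that a non-significant interaction in this phase does not rule out f=.16.

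This is a text change and needs no extra participants. Its one cost is that the stated power for this phase at f=.16 will look much less favourable than the full-trial figure.

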### **Data Analysis Plan**

All data will be initially tested for normality, outliers, and errors. We will then compute summary statistics and derive across-group statistical comparisons to identify any demographic variables, such as age, gender, education, or cognitive frailty, group differences after the randomization process. If group differences are detected for a variable, all analyses will include that variable as a covariate. We will also present primary and secondary outcome measures using descriptive statistics, summarize categorical variables using frequencies and proportions, and report descriptive statistics as medians and interquartile ranges.

***Analyses of Primary and Secondary Cognitive Outcomes.*** Outcomes will be tested according to the intention-to-treat principle with analysis of variance, evaluating both the changes from baseline to the completion of training (immediate treatment effects) and the changes from baseline to +6mo after training (retention effects). All analyses will be conducted on the baseline-normed Blom transformed scores for each measure, an approach used in prior intervention research on older adults. Composite cognitive scores (for each cognitive outcome) will be formed by averaging these scores. Therefore, we shall conduct all statistical analyses on one composite cognitive score representing the primary outcome (episodic memory) and one composite score representing the secondary outcome. There will be, for both outcomes, three composite scores- one for each Assessment (A, B and C). Specific Aim 1 focuses on the increases in cognition between the three training arms at both immediate post-testing and +6mo period. Change scores for each composite score for each individual will first be plotted to evaluate the treatment-related cognitive benefits. We will then examine the composite scores for the primary outcome using repeated measures ANOVA, with Training Arms (3: Low-C, High-C, High-C+) as a between-subject factor and Assessment (2) as a within-subject factor, for both immediate post-training gains (Assessments A and B) and for long-term retention of these gains (Assessments A and C). Of main

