interest is the interaction between the Training Arms and Assessments. To evaluate the extent of immediate post-test cognitive gains across the three training arms, we will conduct pairwise contrasts between High-C and High-C+. Similar analysis will be conducted for the secondary outcome. The two ANOVAs will be adjusted to  $p < .025$  ( $= .05/2$ ) to adjust for multiple comparisons.

Additional analyses will investigate how *cognitive frailty*, as measured by MOCA and MMSE, interacts with training difficulty (High-C vs. High-C+) and extent of transfer, because cognitively fit older adults show faster learning rates for complex skills and working memory. We predict that older adults with greater cognitive frailty will exhibit less cognitive plasticity and therefore will benefit most from moderate attentional control training (High-C), whereas older adults with higher cognitive functioning will find the most challenging training dose (High-C+) to be most beneficial and exhibit greatest cognitive plasticity.

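### The power of more than 87% given for the corrected .025 level holds for the immediate post-training test (N=144, about 89%) but not for the 6-month retention test (N=117, about 80%), at f=.16 and an assumed correlation of .5

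*Combined protocol and SAP*

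**What the plan says.** The paragraph on sample size justification for the older adults (Study Design) reports power from G*Power 3.1 for the interaction of three training arms with two assessments. It says openly that power is calculated for the full trial and that this study is a first phase with a requested sample of 51. Two effect sizes are given: f=.35 from the pilot studies, and f=.16, "based on a meta-analysis on computer-based cognitive training in older adults".

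Three statements matter here:

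- Baseline versus immediate post-training (A vs B): "The proposed total sample size of 144 older adults will provide us with" more than 93% power at f=.16 and p<.05.
- Baseline versus 6 months (A vs C): "we expect to retain a total of 117 older adults", allowing for roughly 20% "attrition between Assessments B and C". This gives more than 87% power at f=.16 and p<.05.
- Corrected level: "Our proposed sample size will provide us with sufficient power" (more than 87%) for the interaction at .025, that is .05 divided by two cognitive outcomes. This sentence names no N, effect size, correlation or pair of assessments.

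The Data Analysis Plan specifies a repeated-measures ANOVA with "Training Arms (3: Low-C, High-C, High-C+) as a between-subject factor and Assessment (2) as a within-subject factor", to be run "for both immediate post-training gains (Assessments A and B) and for long-term retention of these gains (Assessments A and C"). It then says "The two ANOVAs will be adjusted to" p<.025. The Protocol Synopsis makes performance at the 6-month retention period part (b) of the primary objectives.

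**The concern.** The only power figure given expressly for the retention comparison is at p<.05, while the analysis plan sets the ANOVAs at .025. The sentence that moves to .025 repeats the same 87%. With N, effect size and alternative fixed, lowering alpha from .05 to .025 must reduce power, so one figure cannot describe N=117 closely at both levels.

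Retention belongs to the primary objectives. A reader planning or funding the full trial would take the chance of missing a true f=.16 effect at 6 months to be below 13%. If the retention test is run at .025, that chance is nearer 20%.

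**Working it through.** **Inputs from the documents.** Three arms (k=3), two assessments per ANOVA (m=2), f=.16 and .35, N=144 for A vs B, N=117 for A vs C, alpha .05 and .025. For this phase, the sample size paragraph gives 51, and the Synopsis and the design overview give 30.

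**Assumptions.** The correlation between repeated measures (rho) and the allocation ratio are not stated. I take rho=.5 and equal arms.

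**Formula** (within-between interaction, noncentral F):

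- lambda = f² × N × m / (1 − rho)
- df1 = (k − 1)(m − 1) = 2; df2 = (N − k)(m − 1) = N − 3
- power = P(F′(df1, df2, lambda) > critical F at alpha)

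**Step 1: reproduce the plan's figures at .05, f=.16.**

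- N=144: lambda = .0256 × 144 × 2 / .5 = 14.75; df 2, 141; critical F 3.06; power **93.5%** (stated: more than 93%).
- N=117: lambda = .0256 × 117 × 2 / .5 = 11.98; df 2, 114; critical F 3.08; power **87.4%** (stated: more than 87%).

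Both reproduce.

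**Step 2: change only alpha, to .025.**

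| Comparison | N | Critical F | Power, f=.16 | Power, f=.35 |
|---|---|---|---|---|
| A vs B | 144 | 3.79 | **89.1%** | near 100% |
| A vs C | 117 | 3.81 | **80.4%** | near 100% |

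The retention figure is 87.4 − 80.4 = 7.0 points below its value at .05. About 137 participants at 6 months would be needed for 87% at .025, against the 117 expected.

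**Step 3: sensitivity to the unstated correlation (f=.16).**

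| rho | N=144, .05 | N=117, .05 | N=144, .025 | N=117, .025 |
|---|---|---|---|---|
| .40 | 88.4% | 80.4% | 81.8% | 71.5% |
| .49 | 93.1% | 86.7% | 88.4% | 79.5% |
| .50 | 93.5% | 87.4% | 89.1% | 80.4% |
| .51 | 94.0% | 88.1% | 89.8% | 81.3% |
| .575 | 96.7% | 92.3% | 93.9% | 87.2% |
| .60 | 97.5% | 93.8% | 95.3% | 89.4% |

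At .49 the N=117 figure at .05 drops below the stated 87%. For N=117 to reach 87% at .025, rho must be about .57. The figures at .05 would then be about 96.6% and 92.1%, a poor match to the printed 93 and 87.

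**Step 4: the same calculation for this phase (alpha .025, rho=.5).**

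- N=51: 37.9% at f=.16; 98.7% at f=.35.
- N=30: 20.2% at f=.16; 84.6% at f=.35.

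**The case against.** The strongest defence is that the sentence at .025 is true as written. The paragraph attaches the word proposed to the 144, whereas the 117 are participants it expects to retain. If the sentence means 144, power at .025 is 89.1% and more than 87% is correct. That reading is fair, so a reader who infers that the plan makes a plainly false statement about retention goes further than the text allows. The reading still leaves retention with no power figure at .025. The sentence also follows directly on the A vs C calculation and does not limit itself to A vs B. The repeated 87% may have been carried over from the N=117 line, but that is inference.

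Second, every stated power is a lower bound and the correlation is not given. With rho at about .575 or above, all three bounds at f=.16 are literally true. One bound in the paragraph is certainly loose: more than 98% at f=.35 and N=144, where rho=.5 gives close to 100%. So rho=.5 is likely rather than established. It remains much the better fit to the two f=.16 figures.

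Third, the .025 sentence names no effect size, and at f=.35 the claim holds easily for both comparisons. That stands: the shortfall concerns f=.16 only.

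Fourth, the correction is described as covering two ANOVAs, one per outcome, and the text does not say in terms that it governs A vs C. Applying it there is the natural reading, since the plan runs the same model on both pairs of assessments.

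A reader might also infer that this trial has about a 20% chance of missing an effect at 6 months. The documents do not support that. The 117 belong to the full trial, and the paragraph says so.

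**Conclusion.** The concern holds in a limited form. At f=.16, with rho=.5 assumed, more than 87% power at .025 is right for the immediate post-training comparison (89.1%, N=144) and not for 6-month retention (80.4%, N=117). The type II error for retention in the planned full trial is therefore about 20%, not under 13%.

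The result depends on three things: the assumed correlation, which the documents do not give; the smaller of the two effect sizes; and the reading that .025 applies to the A vs C ANOVA. The practical consequence is modest, since 80% is still a conventional target. The fault is an unqualified sentence and a missing retention figure at the level of the planned test, not a flaw in the design.

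**What to change.** In the sample size justification, replace the single statement at .025 with one figure per comparison at f=.16: about 89% for A vs B with N=144, and about 80% for A vs C with N=117. State the correlation that was used; if it was not .5, recompute both figures. Say that these powers apply to the planned full trial only, and add the figures for this phase at .025: about 38% (f=.16) or 99% (f=.35) with 51 participants, and about 20% or 85% with 30. State in the Data Analysis Plan that .025 applies to the A vs C ANOVA as well as the A vs B ANOVA, if that is the intention.

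The cost is wording only. No sample size, analysis or procedure changes. The downside is that the stated retention power becomes less favourable.
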